3.3 Randomization and Blinding

Patients were randomised in a 1:1 ratio to Spironolactone or control using random permuted blocks stratified by center. Randomisation lists for each center were created by the Study Coordinating Center, KU Leuven, using the statistical software SAS 9.3. Randomisation was carried out via a web-based management system located at KU Leuven. A full randomisation list will be held securely at KU Leuven until data base lock is achieved.

All persons evaluating key tests, the clinical endpoints committee, and those conducting laboratory biomarkers tests were kept blind to the treatment allocation.

3.4 Study Assessments

The study assessment schedule is detailed in appendix 1.

4. STATISTICAL ANALYSIS

4.1 General

Statistical analyses will be carried out using Stata [®] version 15.1. The primary efficacy analyses will be carried out on the Full Analysis Set using the Intention to Treat principle. Missing data will be identified and an effort will be made where possible to obtain the missing values from the original medical records. Data will be checked for outliers and, where possible, outlying values will be validated against the original medical records.

4.2 Interim Analyses

No interim efficacy analyses will be carried out. An independent Data and Safety Monitoring Committee will review safety data throughout the trial and advice on trial modifications or premature stopping for safety.

4.3 Time-Points For Analysis

The original primary efficacy analysis requires measurement of serum levels of PIIINP at baseline and at 9 months. Patients randomised after 1 January 2018 will only achieve a maximum final visit of between 3 and 6 months. For the primary analysis, we will use

samples from the final trial visit provided the visit occurred at least 3 months after randomisation. Other visits are described in the schedule in appendix 1.

4.4 Analysis sets

The Full Analysis Set (FAS) will consist of all randomized patients who receive at least one dose of the study medication. This will be the primary efficacy population. Following the intention-to-treat (ITT) principle, patients will be analysed according to the treatment to which they were assigned at randomization.

The Safety Set (SS) will consist of all patients that received at least one dose of the study drug and had at least one post-baseline safety assessment. Patients will be analysed according to the treatment received.

The Per Protocol Set (PPS) will consist of all randomized subjects without any major protocol violation. Major protocol deviations will be defined prior to un-blinding. Results based on the PPS population will be used to support the primary analysis results. Each analysis population will be defined before unblinding.

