1.3 Study design and population

The study follows a prospective randomized open label blinded evaluation (PROBE) parallel group design. All persons evaluating key tests, the clinical endpoints committee, and those conducting laboratory biomarkers tests will be kept blind to the treatment allocation.

The study will be conducted in approximately 800 patients at increased risk of developing heart failure in approximately 9 centers in the United Kingdom, France, Italy, Ireland, Germany and the Netherlands. Patients will be screened in primary and secondary care. Each center will have its own recruitment strategies under review of local ethics committees.

Inclusion criteria are as follows:

1. Written informed consent obtained prior to the initiation of any study procedures;
2. Age >60 years
3. Clinical risk factors, Either;
 - Coronary artery disease (MI, angioplasty or CABG)

Or at least two of the following;

 - Diabetes Mellitus requiring hypoglycaemic pharmacotherapy
 - Pharmacological treatment for hypertension
 - Microalbuminuria (defined as creatinine > 30mg/g or 3mg/mmol)
 - Abnormal ECG (LVH, QRS >120msec, pathological Q-waves)
4. Biological risk: NT- Pro-BNP values between 125 and 1,000 ng/L or BNP between 35 and 280pg/ml (consistent with ESC guidelines indicating risk of HF but helping to rule out prevalent HF or atrial fibrillation)

Exclusion criteria are described in full in the trial protocol.

All patients randomised before 31 December 2017 will be treated and followed up for a period of nine months. Patients randomised from 1 January 2018 until 30 June 2018 will be followed up for a period of between 3 and 6 months. The final patient visit will occur no later than 30 September 2018.

Patients randomised to the experimental group will receive spironolactone, titrated from 25 mg/day (or every other day in some cases) to 50 mg/day, adapted according to a pre-specified algorithm depending on occurrence/resolution of hyperkalaemia and/or

worsening renal function. Patients randomised to the control group will receive background therapy only. Background therapy may include any agent other than loop diuretics or potassium saving diuretics including mineral-corticoid antagonists (angiotensin converting enzyme inhibitors, angiotensin receptor blocker inhibitors, beta blockers and thiazide or thiazide-like diuretics).

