4.7 Primary Endpoint Analysis

The analysis of the primary end-point PIIINP (change from baseline to the final visit) will be carried out using analysis of covariance (ANCOVA). A linear regression model will be fitted,

including a binary variable to indicate the treatment group (placebo/spironolactone), a binary variable to indicate the baseline Gal-3 group (below/above median) and baseline PIIINP. An interaction term will be included to evaluate the additional impact of spironolactone in the elevated Gal-3 group. Residual analysis will be used to examine the fit of the model to the assumptions of linear regression and data may be transformed to meet the assumptions of linear regression.

As this is a proof of concept trial additional exploratory analyses will be carried out for the primary outcome. In particular Gal-3 will be considered categorised into thirds i.e. cut at the tertiles of the distribution, and treated as a continuous variable. Both of these methods may provide gains in power to detect an interaction compared to treating Gal-3 as elevated or not based on the median value.

The ANCOVA model analysing change in PIIINP requires PIIINP to be available at both the baseline and final visit. If a patient is missing PIIINP at either baseline or final visit they are automatically dropped from the analysis. Sensitivity analyses will be carried out using multiple imputation with chained equations to impute missing baseline and/or final visit values.

An alternative approach to the standard ANCOVA analysis for clinical trials with a single follow-up measure of the outcome plus a baseline measure, was proposed by White and Thompson [2005]. This method includes the baseline measure as an additional outcome, constrained to have the same mean in both groups and allowed to be correlated with the follow-up measurement. In the absence of missing data this model produces identical effect estimates to the ANCOVA model and almost identical standard errors. In the presence of missing baseline data this model has the advantage of being able to include patients with a follow-up measurement of the outcome but who are missing a baseline measure. This method may therefore allow gains in statistical power in the presence of missing data.

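### The Full Analysis Set and Safety Set require a dose of study drug that controls never receive; if controls are let in anyway, never-dosed patients leave the spironolactone arm only, against the stated ITT principle

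*SAP*

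**What the plan says.** Section 4.4 makes the FAS the primary efficacy population and sets its entry rule: "The Full Analysis Set (FAS) will consist of all randomized patients who receive at least one dose of the study medication". It then adds: "Following the intention-to-treat (ITT) principle, patients will be analysed according to the treatment to which they were assigned at randomization". Section 4.1 repeats the commitment: "The primary efficacy analyses will be carried out on the Full Analysis Set using the Intention to Treat principle".

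The Safety Set, also in 4.4, begins: "The Safety Set (SS) will consist of all patients that received at least one dose of the study drug". It further requires a post-baseline safety assessment and groups patients by treatment received. Neither definition has a clause for controls. The section closes with: "Each analysis population will be defined before unblinding".

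Section 1.3 describes an open-label design and says: "Patients randomised to the control group will receive background therapy only". In the Appendix 1 visit schedule the only dispensing row is for spironolactone, starting at the inclusion visit (M0), where randomisation also takes place.

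The primary model in 4.7 has terms for treatment, baseline Gal-3 group and baseline PIIINP, and: "An interaction term will be included to evaluate the additional impact of spironolactone in the elevated Gal-3 group".

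**The concern.** A dosing condition works as an entry rule when both arms are given something to take. Here only one arm is. The criterion therefore either empties the control arm or, once controls are admitted by implication, acts on the spironolactone arm alone.

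The second outcome is the one likely to occur in practice. Patients and sites know the allocation, so whether a first dose is taken can depend on it and may be related to prognosis. The document neither shows nor excludes that. Removing non-starters from one arm gives up the comparability that randomisation provides. Analysing the remaining patients as randomised does not bring back those already removed.

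At stake is which patients form the primary dataset, and with them the treatment and treatment-by-Gal-3 estimates. In the Safety Set the only defect is that controls have no route in, which would leave no comparator. Its as-treated grouping and its omission of never-dosed spironolactone patients are not in dispute.

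**Working it through.** **1. The text side by side**

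| Reading of 4.4 | Controls in FAS (N=500) | Spironolactone in FAS | Problem |
|---|---|---|---|
| Literal | 0 of about 250 | dosed patients only | treatment and interaction terms not estimable |
| Controls admitted, dose rule kept | all | dosed patients only | one-arm exclusion after randomisation |
| ITT overrides the dose rule | all | all | a stated criterion is ignored |

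**2. The plan's own figures**

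Inputs from section 3.2: residual SD 1.73 µg/l, two-sided 5%; 800 patients for an interaction of 0.79 at 90% power; 500 patients for 0.87 at 80% or 1.0 at 90%. With four equal cells, N = 16 × SD² × (z₀.₉₇₅ + z_power)² / δ².

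- δ = 0.79, 90%: N = 806, against 800.
- δ = 0.87, 80%: N = 497, against 500.
- δ = 1.0, 90%: N = 503, against 500.

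The figures reproduce. At N=500 (125 per cell) the interaction SE is 1.73 × √(4/125) = 0.3095 µg/l, and power for 0.87 is 80.3%.

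**3. Effect of dropping never-starters from one arm**

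The SAP gives none of the following, so they are assumptions: never-started share p = 2–5%; share s of never-starters with a final sample = 1, 0.5 or 0; outcome difference from starters = 0.5 SD = 0.865 µg/l.

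Number excluded: 250 × 0.02 = 5; 250 × 0.05 = 12.5.

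Never-starters as a fraction of the sampled arm: f = ps / (1 − p + ps). Arm-mean shift = f × 0.865. For the interaction the worst allocation puts all never-starters in one Gal-3 half, which replaces p by 2p.

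| p | s | Arm-mean shift (µg/l) | Interaction shift, all in one half (µg/l) | % of 0.87 | In SE (0.3095) |
|---|---|---|---|---|---|
| 2% | 1 | 0.017 | 0.035 | 4.0 | 0.11 |
| 5% | 1 | 0.043 | 0.087 | 9.9 | 0.28 |
| 2% | 0.5 | 0.009 | 0.018 | 2.0 | 0.06 |
| 5% | 0.5 | 0.022 | 0.046 | 5.2 | 0.15 |
| either | 0 | 0 | 0 | 0 | 0 |

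If never-starters are spread evenly over the two halves, the interaction does not shift. The s = 0 row follows from 4.7: "If a patient is missing PIIINP at either baseline or final visit they are automatically dropped from the analysis". Never-starters without a final sample therefore leave the complete-case ANCOVA under either definition. The definition matters for those who stay in follow-up and for the multiple-imputation sensitivity analysis.

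**4. Power cost of keeping never-starters**

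Assume they have no treatment effect and are spread evenly. Diluted interaction = 0.87 × (1 − f); SE = 1.73 × √(2/125 + 2/(125(1 − p + ps))). If never-starters are excluded, the effect stays at 0.87 and s is set to 0 in the SE.

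| p | s | Diluted effect (µg/l) | Power, kept | Power, excluded | Loss (points) |
|---|---|---|---|---|---|
| 2% | 1 | 0.853 | 78.7% | 79.9% | 1.2 |
| 5% | 1 | 0.827 | 76.1% | 79.2% | 3.1 |
| 2% | 0.5 | 0.861 | 79.3% | 79.9% | 0.6 |
| 5% | 0.5 | 0.848 | 77.7% | 79.2% | 1.6 |

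Losses are taken from unrounded powers.

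**The case against.** The strongest reply is that nobody could intend a set without controls. Analysis by assigned arm in 4.4, baseline tables by randomised group in 4.5 and a two-group treatment variable in 4.7 all presuppose two arms. That is right: the empty control arm is a defect of the literal text and not an analysis anyone would run. Two realistic readings remain, and they give different primary populations.

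Section 4.7 also labels the comparator placebo, although 1.3 describes none. This suggests wording carried over from a placebo-controlled template, which would make the matter a drafting slip. The document does not show its origin, and a slip in the primary population still needs correcting.

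A third point is that 4.4 spells out ITT only as grouping by assigned arm, so the conflict depends on the fuller meaning that includes everyone randomised. That is fair as far as it goes, but a dose rule that can act in one arm only is a weakness whatever it is called.

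The closing sentence of 4.4 could be read as deferring the definition. It promises a later step but does not withdraw the criterion already written.

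Finally, the rates are assumptions, first dispensing is at M0 so few may fail to start, and the largest shift needs several unfavourable conditions together. The bias and power figures also use different allocations: under an even spread, keeping never-starters costs some power and removes no interaction bias. All of this stands, and it limits the size of the problem, not its existence.

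**Conclusion.** The concern holds. The entry rules for the FAS and the Safety Set cannot be met by the control arm described in 1.3. The natural repair, admitting controls and keeping the dose rule, produces a one-arm exclusion that contradicts the claimed ITT principle. This conclusion rests on the text alone and is firm.

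The size is uncertain and probably small. The interaction shift ranges from zero to 0.087 µg/l (0.28 SE) under the assumptions of 2–5% never starting and a 0.5 SD difference. That range is an illustration and not a general bound, and no material bias has been shown. The point should be fixed because it leaves the primary population unsettled, not because a large error is expected.

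**What to change.** Rewrite the two definitions in 4.4:

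- **FAS:** all randomised patients, analysed in the arm assigned, whether or not spironolactone was taken, with missing PIIINP handled as in 4.7 and 4.9.
- **Safety Set:** control patients, plus spironolactone-arm patients with at least one dose, each with at least one post-baseline safety assessment. The as-treated grouping can stay.

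The comparator label in 4.7 should be brought into line with 1.3 at the same time.

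No new data are needed. The price is some dilution from patients who never start: 0.6–1.6 power points if half of them are sampled and 1.2–3.1 if all are, relative to admitting controls and dropping never-dosed patients.

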4.5 Screening and Baseline Characteristics

The baseline characteristics of patients who were screened, but who were not included in the trial (either refused or ineligible) will be summarized along with reasons for refusal or ineligibility. It is recognised that only a limited set of baseline characteristics will be collected for these patients. Baseline characteristics will be described for all included and randomised patients by randomised group. Categorical variables will be summarised using frequencies and percentages, and continuous variables using mean and standard deviation (SD) or median and interquartile range (IQR) as appropriate. The number and percentage of patients with missing data will be reported for each variable.

4.6 Patient Disposition, Adherence and Follow-up

The number and percentage of patients screened, randomised and achieving each visit will be reported. Adherence to randomised treatment will be summarized. The number, percentage and type of protocol deviations and violations will be reported. The number of patients withdrawing prematurely from the study or lost to follow-up will be summarised and reported along with the reasons for withdrawal or loss to follow-up.

4.7 Primary Endpoint Analysis

The analysis of the primary end-point PIIINP (change from baseline to the final visit) will be carried out using analysis of covariance (ANCOVA). A linear regression model will be fitted,

including a binary variable to indicate the treatment group (placebo/spironolactone), a binary variable to indicate the baseline Gal-3 group (below/above median) and baseline PIIINP. An interaction term will be included to evaluate the additional impact of spironolactone in the elevated Gal-3 group. Residual analysis will be used to examine the fit of the model to the assumptions of linear regression and data may be transformed to meet the assumptions of linear regression.

As this is a proof of concept trial additional exploratory analyses will be carried out for the primary outcome. In particular Gal-3 will be considered categorised into thirds i.e. cut at the tertiles of the distribution, and treated as a continuous variable. Both of these methods may provide gains in power to detect an interaction compared to treating Gal-3 as elevated or not based on the median value.

The ANCOVA model analysing change in PIIINP requires PIIINP to be available at both the baseline and final visit. If a patient is missing PIIINP at either baseline or final visit they are automatically dropped from the analysis. Sensitivity analyses will be carried out using multiple imputation with chained equations to impute missing baseline and/or final visit values.

An alternative approach to the standard ANCOVA analysis for clinical trials with a single follow-up measure of the outcome plus a baseline measure, was proposed by White and Thompson [2005]. This method includes the baseline measure as an additional outcome, constrained to have the same mean in both groups and allowed to be correlated with the follow-up measurement. In the absence of missing data this model produces identical effect estimates to the ANCOVA model and almost identical standard errors. In the presence of missing baseline data this model has the advantage of being able to include patients with a follow-up measurement of the outcome but who are missing a baseline measure. This method may therefore allow gains in statistical power in the presence of missing data.

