2. STUDY OBJECTIVES

2.1 Primary Objective

The primary objective of the HOMAGE trial is to investigate whether spironolactone can favourably alter extra-cellular matrix remodelling, assessed by changes in the fibrosis biomarker Procollagen Type III N-Terminal Peptide (PIIINP), in patients at increased risk of developing heart failure and whether this effect is greater in patients with increased plasma concentrations of Gal-3.

The primary outcome measure is change in serum concentrations of PIIINP (RI assay, central lab) from baseline to nine months or final visit (3-6 months in patients randomized after 1st January 2018). Three to nine months is thought to be a period sufficient to influence cardiac fibrosis for which PIIINP is a widely accepted marker. Sensitivity analyses will be carried out for the primary endpoint including only patients who achieved the 9 month visit. Further sensitivity analyses will be carried using PIIINP results at the 1 month visit.

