4.8 Secondary Endpoints

Secondary endpoints will be analysed using ANCOVA for continuous endpoints or multivariable logistic regression or multivariable Cox regression in the case of dichotomous and time to event endpoints respectively.

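### The primary ANCOVA omits centre, the only randomisation stratifier, and the secondary ANCOVAs name no centre term, so precision is lost if PIIINP change differs between centres

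*SAP*

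**What the plan says.** - **Randomisation (SAP 3.3):** 1:1 allocation "using random permuted blocks stratified by center". No other stratification factor is named.
- **Primary model (SAP 4.7):** a linear regression on a treatment indicator, "a binary variable to indicate the baseline Gal-3 group (below/above median) and baseline PIIINP". On the interaction it adds: "An interaction term will be included to evaluate the additional impact of spironolactone in the elevated Gal-3 group". The covariate list is written out in full and centre is not in it.
- **Secondary models (SAP 4.8):** "Secondary endpoints will be analysed using ANCOVA for continuous endpoints", with logistic or Cox regression for the other endpoint types. No covariates are listed.
- **Objective (SAP 2.1):** two questions. The first is "whether spironolactone can favourably alter extra-cellular matrix remodelling", which is an overall treatment effect. The second is whether the effect is larger at higher Gal-3.
- **Setting (SAP 1.3):** "approximately 9 centers in the United Kingdom, France, Italy, Ireland, Germany and the Netherlands", with patients screened in both primary and secondary care. "Each center will have its own recruitment strategies under review of local ethics committees".

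Centre appears nowhere else in the analysis sections as a fixed effect, random effect or sensitivity analysis, and no reason for leaving it out is given.

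**The concern.** Blocking within centre keeps the arms balanced on centre, so differences between centres drop out of the true sampling error of the overall treatment effect. A model without centre does not know this. It leaves the between-centre variance in the residual and reports a standard error that is too large. The overall effect is the first half of the primary objective and the main contrast in the secondary ANCOVAs.

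The interaction is affected differently. Gal-3 was not a stratifier, so the treatment-by-Gal-3 cells are not balanced within centre. Without centre in the model, that test is valid but less efficient than it could be.

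Efficiency matters in this trial. SAP 3.2 lowers the target from 800 to 500 patients because of recruitment difficulty and looks to the method of analysis for extra power. Centre is known for every patient and is not mentioned as a source of such a gain.

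**Working it through.** **Inputs from the SAP.** Residual SD 1.73 µg/l; 800 patients for an interaction of 0.79 µg/l at 90% power; 500 patients for 0.87 µg/l at 80% power or 1.0 µg/l at 90%; two-sided 5% (all 3.2); about 9 centres (1.3); 1:1 blocks within centre (3.3).

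**Assumptions.** The share ρ of residual variance lying between centres is not in the SAP; 0, 5, 10 and 20% are used. The SD of 1.73 is read as including any centre variance. The block size is taken as 4 in the simulation.

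**1. Reproducing the plan's figures.** With four equal cells, SE(interaction) = 4·SD/√N.

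- N for 0.79 at 90% power: 16 × 1.73² × (1.96 + 1.2816)² / 0.79² = 806, against the stated 800.
- At N = 500, SE = 4 × 1.73/√500 = 0.3095. Power for 0.87 is Φ(0.87/0.3095 − 1.96) = 80.3%; for 1.0 it is 89.8%.

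The plan's figures hold.

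**2. Overall treatment effect.** SE without centre = 2 × 1.73/√500 = 0.1547, so the 95% half-width is 1.96 × 0.1547 = 0.303 µg/l. With centre in the model the SE is multiplied by √(1 − ρ). Since the true sampling error is already the smaller figure, the unadjusted test has type I error 2·[1 − Φ(1.96/√(1 − ρ))].

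| ρ | SE ratio | Half-width with centre (µg/l) | Type I error without centre |
|---|---|---|---|
| 0% | 1.000 | 0.303 | 5.0% |
| 5% | 0.975 | 0.296 | 4.4% |
| 10% | 0.949 | 0.288 | 3.9% |
| 20% | 0.894 | 0.271 | 2.8% |

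A simulation (9 equal centres, N = 500, 6000 runs per setting, terms centred so that the treatment coefficient is the overall effect) gave mean model SEs with centre of 0.1549, 0.1511, 0.1470 and 0.1387, against about 0.155 throughout without it. Simulated type I error without centre was 5.1, 4.7, 3.8 and 2.9%; with centre it was 4.9 to 5.2%.

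**3. Interaction.** The same simulation gave the mean SEs below. They include the cost of estimating eight extra centre parameters. Power is Φ(0.87/SE − 1.96).

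| ρ | SE without | SE with | Power without | Power with |
|---|---|---|---|---|
| 0% | 0.3098 | 0.3123 | 80.2% | 79.6% |
| 5% | 0.3102 | 0.3047 | 80.1% | 81.5% |
| 10% | 0.3100 | 0.2964 | 80.1% | 83.5% |
| 20% | 0.3103 | 0.2796 | 80.1% | 87.5% |

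Type I error of the interaction test without centre was 5.0 to 5.1% at every share. At ρ = 0, adding centre raises the interaction SE by 0.8% (0.3123/0.3098).

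**4. Unequal centres.** With 10 to 130 patients per centre, the overall SE ratios were 0.975, 0.949 and 0.894 at 5, 10 and 20%. Simulated interaction power rose from 79.7 to 80.7%, 80.5 to 83.9% and 80.4 to 87.5%.

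**5. The other reading of the SD.** If 1.73 is a within-centre SD, leaving centre out inflates it to 1.73/√(1 − ρ). Ignoring the small parameter cost, interaction power for 0.87 at 500 patients then falls from 80.3% to 78.2, 76.0 and 71.0% at 5, 10 and 20%. The direction is the same and the size similar or larger.

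**The case against.** The strongest reply is that the size rests on an assumption. Nothing in the SAP supports a centre share of 10 or 20%. PIIINP is assayed in a central laboratory and baseline PIIINP is in the model, so much of what separates centres may already be absorbed. Local recruitment strategies suggest different patients and baseline levels more than different changes after baseline adjustment. At a 5% share the gain in interaction power is only about one point, and at zero the change costs about half a point. This stands, and it is why the point is minor.

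Second, the sample size is built on the interaction, and that test is neither biased nor inflated. This also stands. The loss is of precision, not validity.

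Third, the type I errors in step 2 belong to the overall effect. With ordinary 0/1 indicators and an interaction, the printed treatment coefficient is the effect in patients below the Gal-3 median. Blocking balances that contrast only partly: its true variance is (1 − ρ/2) of the model variance. Its type I error would be about 4.7, 4.4 and 3.9% at 5, 10 and 20%. This is correct, but 2.1 asks about the overall effect, for which the figures in step 2 apply.

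Last, 4.8 is silent on all covariates, so centre was not specifically excluded there. That is so. Silence still leaves the choice open, and measures such as echocardiography and the shuttle walk are performed at the visits, where a central PIIINP assay gives no protection against centre differences.

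**Conclusion.** The concern holds as a matter worth considering. The SAP stratifies by centre and then analyses without it in the primary model, and it names no centre term for the secondary ANCOVAs. If centres differ in PIIINP change, inference on the overall effect is conservative and the interaction test gives up some power. No bias or type I inflation follows. For PIIINP the likely size is at the lower end of the range: at a 5% share, a confidence interval about 3% wider than needed and roughly one point of interaction power. That the omission exists is certain. How much it costs is not, because it depends on a between-centre variance that the SAP does not give.

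**What to change.** Before unblinding, amend 4.7 to include centre as fixed effects in the primary ANCOVA, with very small centres pooled by a rule stated in advance. In 4.8, name centre as a covariate in the secondary ANCOVAs. The below/above-median Gal-3 interaction stays as the primary interaction test.

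The change is to SAP wording only and uses a variable already recorded for every patient. It takes about 8 of roughly 495 residual degrees of freedom, and the t critical value is 1.9648 either way. If centres turn out not to differ, about half a point of interaction power is lost. If the sponsor prefers to leave centre out, the SAP should say why.

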3.2 Sample Size

Sample size calculations determined that 800 patients were required to detect an interaction term of $0.79\mu\text{g/l}$ in PIIINP with a two sided significance level of 5% and 90% power. A residual standard deviation of PIIINP of $1.73\mu\text{g/l}$ was assumed based on results from Kosmala M et al. JACC 2011: 4:1240.

The sample size was calculated using the formula for testing interactions in analysis of variance - see Lachenbruch P, (1988) Statistics in Medicine, (7) 467-469. The interaction term represents the difference in the effect of Spironolactone on PIIINP in patients with or without an elevated Gal-3 (below/above median value).

The sample size of 800 patients will provide sufficient statistical power for exploratory analyses of the main secondary endpoints listed above. For example, the trial will have 92%-power to find significant, at the 5%-alpha error level, a difference of $15\ \mu\text{g/l}$ for PICP and 78%-power to find significant a difference of $1.1\ \text{m/s}$ for E/E' ratio.

Due to difficulty with patient recruitment updated sample size calculations were carried out in March 2018. It was determined that 500 patients would provide 80% power to detect an

interaction of $0.87\mu\text{g/l}$ in PIIINP with a two sided significance level of 5% (or 90% power to detect an interaction of $1.0\mu\text{g/l}$ in PIIINP). Gains in statistical power may be gained attained through the method of analysis, in particular through treating GAL-3 as a continuous variable and using methods for repeated measurements.

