4.10 Multiple Comparisons

There are no planned adjustments to the Type 1 error for multiple comparisons.

REFERENCES

2. Lachenbruch PA: A note on sample size computation for testing interactions. *Stat Med* 1988, 7(4):467-469.

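### Does section 4.7 leave the overall effect of spironolactone on PIIINP without an analysis?

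*SAP*

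**What the plan says.** SAP section 2.1 sets a primary objective in two parts. The first is "whether spironolactone can favourably alter extra-cellular matrix remodelling", measured by change in PIIINP in patients at increased risk of heart failure. The second is "and whether this effect is greater in patients with increased plasma concentrations of Gal-3".

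Section 4.7 gives the analysis in two consecutive sentences. One describes a linear regression with a binary treatment variable, a binary Gal-3 variable split at the median, and baseline PIIINP. The next reads: "An interaction term will be included to evaluate the additional impact of spironolactone in the elevated Gal-3 group". The coding of the binary variables is not given, and no overall or averaged treatment contrast is named. The exploratory analyses in that section (Gal-3 in thirds, Gal-3 as continuous) are justified by power for the interaction.

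Section 3.2 sizes the trial on the interaction alone: "The interaction term represents the difference in the effect of Spironolactone on PIIINP in patients with or without an elevated Gal-3". Section 4.10 adds: "There are no planned adjustments to the Type 1 error for multiple comparisons".

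**The concern.** Section 4.7 gives a purpose only to the interaction term, although section 2.1 puts the overall effect first. Suppose a reader takes section 4.7 to mean one model, codes both variables 0/1 and makes below-median Gal-3 the reference. The model for the expected outcome is then b0 + b1·treatment + b2·Gal-3 + b3·treatment·Gal-3 + b4·baseline. Here b1 is the effect of spironolactone in low Gal-3 patients, not in the trial as a whole. That coefficient rests on half the patients and, under the hypothesis in section 1.2, on the half expected to respond less.

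If b1 were reported as the treatment effect, the first part of the objective would be answered with a larger standard error and for the wrong population. Leaving the contrast unnamed also seems to leave room to choose it after the results are known.

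**Working it through.** **Inputs.** From section 3.2: residual SD 1.73 µg/l, two-sided 5% level, 800 patients originally and 500 after the March 2018 update. From section 3.3: 1:1 allocation. The median split gives two Gal-3 halves, so four cells of about N/4. The SAP gives no overall effect size; the values 0.4 and 0.5 µg/l below are assumptions.

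**1. The plan's own figures.** The interaction is a difference of two differences, with SE = SD·√(16/N).
- N for 0.79 µg/l at 90% power: 16 × 1.73² × (1.960 + 1.282)² / 0.79² ≈ 806, against 800 stated.
- At N = 500, SE = 1.73 × √(16/500) = 0.309. Power for 0.87 is Φ(0.87/0.309 − 1.96) = 80.3%, and for 1.0 it is 89.8%. The SAP states 80% and 90%.

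The figures reproduce. They concern the interaction only and do not depend on how the overall effect is extracted.

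**2. The two quantities that could be confused, at N = 500.**
- Low Gal-3 coefficient b1: SE = 1.73 × √(8/500) = 0.219.
- Average of the two Gal-3 group effects, b1 + b3/2: SE = 1.73 × √(4/500) = 0.155.

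**3. Cost of confusing them.** A like-for-like comparison needs both to estimate the same value, that is, a uniform effect d. Power ≈ Φ(d/SE − 1.96).

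| d (µg/l, assumed) | b1 misread as overall | Overall contrast |
|---|---|---|
| 0.4 | 45% | 73% |
| 0.5 | 63% | 90% |

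This is the cost of a misreading, not of anything the plan prescribes.

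**4. Does it matter which legitimate overall estimate is used?** The candidates are the treatment coefficient from the ANCOVA without the product term, and b1 + b3/2 from the model with it.
- Leave baseline PIIINP aside. The main-effects model weights each Gal-3 group's effect by (treated × control)/(group size). With 250 per arm and 250 per Gal-3 half, k treated in the low half forces 250 − k treated in the high half. Both weights are then k(250 − k)/250, so the main-effects estimate is the simple average. Only baseline adjustment, ties or missing values can separate the two.
- Chance imbalance hardly affects precision. With cells of 130/120 and 120/130, SE = 0.5 × 1.73 × √(2/130 + 2/120) = 0.1549, against 0.1547 when balanced. It therefore matters little that randomisation is stratified by center and not by Gal-3.
- The model was simulated with 500 patients, baseline adjustment, and true effects of 0 (low) and −0.87 (high), so a true average of −0.435. Over 4,000 trials the main-effects coefficient and the averaged contrast both had mean −0.437 and SD 0.156.

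**5. The wording.** The first sentence of the model description, taken alone, is a main-effects ANCOVA whose treatment coefficient is the overall effect. The second adds a term for the additional impact in the high Gal-3 group, which presupposes an impact already estimated. That order matches section 2.1: effect first, then whether it is greater with high Gal-3.

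**The case for a change.** The strongest case for a change is that section 4.7 exists to specify the primary analysis, yet one half of the primary objective has no named estimator. Several readings are possible, the trial is open label, and the remedy would be a sentence or two. The omission is real: the text does not settle between one model and two steps, and it states no coding.

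The consequences do not follow from it. The power loss requires an unstated coding and then a misreading of b1 as an overall effect. A statistician fitting this ANCOVA knows that a lower-order coefficient is conditional once a product term is present. Effect coding, centring or an ANOVA-type main-effect test would give the average directly.

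More striking contrasts can be built by letting the effect differ by Gal-3. With 0 in the low group and 0.87 in the high group, b1 rejects 5% of the time and the overall contrast 80%. These are tests of two different true values, 0 and 0.435, and a 5% rejection rate is correct when the low Gal-3 effect is zero. Such pairs do not measure a loss for one quantity.

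The worry about choosing after the fact is weak because the two sensible estimates are near-identical.

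One could also ask for a stated order of the two tests. Type 1 error inflation would arise only if success on either question counted, and the SAP contains no such rule. Section 3.2 points to the interaction as the driving test, and section 4.10 openly declines adjustment in a proof-of-concept trial. A fixed order would make the second question conditional on the first. That is a fair trade-off, not an error.

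**Conclusion.** No change to the plan is needed. Section 4.7 omits a detail: it does not name the contrast for the first part of the section 2.1 objective. An analyst following the plan would supply it from the main-effects ANCOVA or as the Gal-3-averaged contrast, with practically the same estimate and a standard error near 0.155 µg/l at N = 500. Writing the contrast down would be tidy but would alter no estimate, no test of the interaction and no sample size.

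The only like-for-like cost is 45% to 63% power instead of 73% to 90%. It arises only if the low Gal-3 coefficient is mistaken for the overall effect, and it assumes a uniform effect of 0.4 to 0.5 µg/l, a residual SD of 1.73 µg/l and four equal cells. The near-equality of the two overall estimates rests on 1:1 allocation and a median split with few ties or missing Gal-3 values.
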